#### 9.4.1 Nordic National Registers for Sweden, Norway and Denmark

The availability of national registries makes the Scandinavian countries an optimal choice to identify parent-offspring combinations with linked longitudinal records data. Each individual in Sweden, Norway and Denmark is provided with a unique personal identification number at birth or upon immigration. The personal identification number is used for many administrative purposes, such as an identifier in population and health care registers in all three countries. The number forms the basis for the precise linkage of individual-level data between different registers in Sweden, Norway and Denmark, allowing the creation of a database with individual-level data for any given study. The number also allows family linkage of data.

Sweden, Norway and Denmark have National Patient Registers which contain data from in- and outpatient care. The key variables of the patient registries include diagnosis, surgery and other procedures, as well gender, age, region, hospital, specialty, referrals to/treatment in hospitals or by specialists and hospital admissions/discharges. The National Prescription Registries include all prescribed and dispensed medication to the individual patient covering all pharmacy transactions retrospectively from 1995 (Denmark), 2004 (Norway) and 2005 (Sweden). Country-specific information on the registers is provided below.

## Sweden

Individual patient data is collected from both in- and outpatient hospital based specialist care across all of Sweden. The National Patient Register dates back to 1964. From 1987 onward, there is information on all completed inpatient admissions across the country. The collection of outpatient care data began in 2000. The register is updated annually and available from September/October the following year.

All medicines are prescribed electronically in Sweden. The National Prescription Register tracks the full details of all dispensed medications at individual patient-level in Sweden since 01 July 2005. Patients are followed longitudinally through their personal identification number, regardless of which pharmacy they visit. The National Prescription Register is updated monthly and covers all sales of dispensed medication from Swedish pharmacies.

The Medical Birth Register contains information about all pregnancies resulting in delivery in Sweden and is frequently used for quality improvement work and for research. The register contains detailed information about mothers and births. The Swedish Multigeneration Register was established in 1973, and contains information on more than nine million individuals. Data on mothers are available in 97% and on fathers in 95% of index people (those born from 1932 onwards and those alive on 01 January 1961). Individual-level data on breastfeeding is not available in the Swedish registers.

## Norway

In Norway, data about live offspring and their parents are obtained from the Medical Birth Registry, the National Population and Housing Censuses (1960-1990), the Central Person Register, and some other national registers. The database is completely anonymous, in that the 11-digit national identity number has been removed and substituted by another number with no connection to the original number. Thus, it is not possible to connect to micro data from sources outside the database. To further prevent the identification of the individual, parts are replaced with information about birth and home municipality/county. The Medical Birth Registry of Norway holds information on all pregnancies and births since 1967 (notification is compulsory) from 12 completed weeks of gestation onwards. Linkage to fathers is available for 97% of live and non-live births (3). Individual-level data on breastfeeding may not be available in the Norwegian registers.

## Denmark

Denmark has the longest-standing civil registration system in the world. From 1968 and onwards, the Danish Civil Registration System (CPR) has held information on all persons with a permanent address in Denmark, and the relations between spouses, parents and offspring. Therefore, there is considerable scope for creating a multigenerational database that can accommodate multiple research purposes. The National Patient Register holds good quality data on diagnoses of childhood NDD and adults with psychiatric disorders in secondary care. The Danish Medical Birth Register has held near complete information on pregnancy (live and non-live births) and birth details for mothers and offspring respectively since 1973, from 22 completed weeks of gestation onwards. Data on fathers are available for 97.5% of live births (6). Information on breastfeeding is available from 2012 in the Danish registers.

## 9.5 Study Size

The primary objective of this observational study is to explore the association of risk of NDD, including ASD in offspring paternally exposed to valproate.

The trend in the prevalence of developmental disabilities in US children aged 3-17 has been reported to be 13.9% between 1997-2008 (33). While there is a prevalence of approximately 1% total population for ASD globally, developmental intellectual disability ranges from 0.4 to 3% globally. According to a large population-based case-control study (34) using Danish registry data, 3.7% of children aged up to and including 5 years in the control group (unexposed to AEDs) had learning disabilities (defined as mental retardation (ICD-10: F7x), specific developmental disorders (ICD-10: F80–83), ASD (ICD-10: F84), emotional/behavioural disorders (ICD-10: F9x) or having special educational needs). Therefore it is reasonable to assume a background risk in the range of 3-4% for NDD in live offspring.

In this study, the primary endpoint is NDD, including ASD. Given the interest in ASD, the sample size will be estimated for this endpoint, with the assumption that this endpoint is nested within the primary endpoint. Accordingly, the sample size should be sufficient to observe the desired effect size for the composite primary endpoint.

As previously reported, maternal use of valproate during pregnancy is associated with significantly increased risk of ASD (2). According to the observational study conducted in live offspring within Denmark using registry data, risk of ASD after 14 years of follow-up has been estimated to be 1.53% (95% Confidence Interval (CI) 1.47,1.55). In the same study the corresponding risk of ASD in live offspring exposed maternally to valproate has been estimated to be 4.42% (95%CI 2.59, 7.46). The adjusted HR was 2.9 (95%CI 1.7, 4.9). Data from an observational population-based cohort study on risk of ASD in live offspring following paternal use of SSRIs before conception (7), using Nordic registry data, reported an incidence of 1.13% of ASD in live offspring born to fathers who had redeemed a prescription for SSRIs in the last 3 months prior to conception. The incidence rate was 169 per 100,000 person-years. In an unexposed comparator group (no paternal exposure to SSRI) the corresponding incidence rate was 110 per 100,000 person-years. Thus, the incidence rate in the exposed cohort corresponded to a 54% increased risk. After adjustment for potential confounders the HR was 1.43 (95%CI 1.18-1.74).

Using this information the following assumptions will be made for sample size estimation for the ASD endpoint:

- The background incidence of interest will focus on the incidence of ASD in young offspring since this is an outcome of interest within the composite endpoint of NDD. This is assumed to be 1.5%.
- An effect size based on ratio of rates that ranges between 1.5 to 3.0.
- Total births for study period: Norway 2004-2017  $n \sim 0.8M$ ; Denmark 1995-2017  $n \sim 1.3M$ , and Sweden 2005-2017  $n \sim 1.5M$
- Record linkage for family unit of minimum of 95% all births across all countries (6)
- Incidence rate of valproate monotherapy in adults of 1.2/1000 patients (35)
- Incidence of AED therapy and/or diagnosis in children of 0.15% (36)

---

 Based on Swedish national population statistics where the population in this age group is calculated to be 10,117,269 (<http://www.statistikdatabasen.scb.se>) the incidence of initiation in this age group is 0.1%. Since it is possible that children with some forms of epilepsy may not receive AEDs a conservative adjustment of 50% will be made to this incidence estimate such that the period incidence of 0.15% in children aged 0-11 years inclusive,

The minimum desirable sample size should be able to estimate such an effect with an appropriate margin of error. Such uncertainty in the findings will be quantified by calculating a 95% CI around the observed effect measures (HR). CI width will provide an indication of precisions of the point estimate; the upper and lower limit will provide a range of credible values consistent with observed data. Since this study is exploratory and the risk of the outcome in offspring paternally exposed to either valproate (monotherapy) or lamotrigine/levetiracetam (monotherapy remains to be defined, the following sample size calculations presented in Table 6 use a range of effect sizes based around the aforementioned estimates for analogous drug-event associations.

**Table 6: Expected sample sizes to estimate various effect size given different reference risks of ASD in offspring paternally exposed to other AEDs (by power: 90% and 80%)**

Reference Risk of ASD	Effect size											
	1.5	2	2.5	3	3.5	4	1.5	2	2.5	3	3.5	4
	Power: 90%						Power: 80%					
0.5%	42948	12970	6718	4302	3082	2364	32482	9888	5154	3316	2384	1836
1.0%	21346	6440	3334	2132	1526	1170	16144	4910	2558	1644	1182	910
1.5%	14144	4264	2204	1410	1008	772	10700	3252	1692	1088	780	600
2.0%	10544	3176	1640	1048	748	574	7976	2422	1260	808	580	446
3.0%	6944	2086	1076	686	490	374	5254	1592	826	530	380	292
4.0%	5144	1542	794	506	360	274	3892	1178	610	390	280	214

ASD: Autism Spectrum Disorder.

For the ASD endpoint, it is assumed that the risk of ASD in the reference group (live offspring paternally exposed to lamotrigine/levetiracetam monotherapy) is 1.5%. In order to be able to observe a HR of 2.0 (i.e. doubling of risk in offspring paternally exposed to valproate) with 5% significance and 80% power, a sample size of 3253 children within the family linked unit would be needed across all three countries. This requires a minimum of 1627 offspring within a family linked unit with paternal exposure to valproate (monotherapy), and a minimum of 1627 offspring within a family linked unit with paternal exposure to lamotrigine/levetiracetam (monotherapy).

For the primary endpoint, the same assumptions exist with the exception that the assumed risk of NDD (including ASD) in the reference group is 4%. Therefore, in order to be able to observe a HR of 2.0 (i.e. doubling of risk in offspring paternally exposed to valproate) with 5% significance and 80% power, a sample size of 1178 offspring within the family linked unit would be needed across all three countries. This requires a minimum of 589 offspring within a family linked unit with paternal exposure to valproate (monotherapy), and a minimum of 589 offspring within a family linked unit with paternal exposure to lamotrigine/levetiracetam (monotherapy).

The eligible study cohort sizes are projected as follows:

---

diagnosed with epilepsy and/or treated with AEDs can be used for sample size assumptions. Furthermore, since a literature review reveals no equivalent estimates in Norway and Denmark, this estimate will be applied to Norway and Sweden to adjust feasibility counts.

Based on the aforementioned birth rate statistics and an assumption of 95% of births linked to fathers, an incidence rate of valproate monotherapy of 1.2/1000 patients and an incidence of 0.15% for childhood exposure to AEDs and/or diagnosis of epilepsy, we estimate an eligible population of offspring within a linked family unit with paternal valproate exposure of  $n \approx 940$  between 2004-2017 for Norway,  $n \approx 1495$  between 1995-2017 for Denmark, and  $n \approx 1645$  between 2005-2017 for Sweden. The estimated pooled eligible family linked offspring cohort for valproate monotherapy is 4,080 across all three countries.

If these projections are observed, this study should have a sufficient number of paternally exposed valproate offspring within each country to observe a HR of 2.0 for the primary endpoint of NDD, including ASD, with 5% significance and 80% power. It is also anticipated that this study would have a sufficient number of paternally exposed valproate offspring across all three countries to observe a HR of 2.0 for the endpoint of ASD (see sensitivity analysis section 9.7.5)

In accordance with our proposal, the comparative evaluation of CM as a composite outcome will be secondary and therefore sample size estimation does not apply. For completeness an evaluation of the study power for a comparative evaluation based on major CM (since these comprise the smallest subgroup of CM but most serious) is presented below, with the assumption that this outcome is nested within the secondary composite outcome. Accordingly, the sample size should also be sufficient to observe the desired effect size for the comparative analysis of the composite secondary endpoint for Norway and Denmark.

The background incidence of major CM in pregnancies has been estimated to be 37.1 cases per 1000 pregnancies among live births (up to 1 year of age) or stillbirths (37). The combined incidence estimate of major CM associated with maternal valproate exposure (spina bifida, ventricular septal defect, atrial septal defect, cleft palate, hypospadias (boys only) and polydactyly) is 56.6 cases per 1000 pregnancies (17). It is acknowledged that this estimate does not contain all major CM and is therefore an estimate. According to the systematic review by Jentink et al. of 8 studies which explore the risk of major CM associated with valproate exposure in the first trimester compared to other AED, the effect size ranged from OR 2.9 (95% CI 1.1-7.7) for cleft palate to OR 5.5 (95% CI 1.4-25.4) for polydactyly; with the strongest association reported for hypospadias in boys (OR 6.6 (95% CI 2.8-16.6)), although the CI were wide reflecting the small numbers analysed. It would be reasonable to select the smallest effect size in the smallest subgroup of CM (i.e. major) to explore the power of this study to reject the null hypothesis of no difference. Assuming a minimum effect size of 2.5, where the background incidence was 3%, with 80% power, a study with a total sample size of 826 family linked offspring ( $n=413$ ) in the valproate monotherapy group and  $n=413$  in the comparator monotherapy group would be desirable.

For Denmark and Norway, linkage is feasible for approx. 97% for live births, but completeness decreases for non-live births. Assuming a worst case scenario of 50% of pregnancies with record linkage, it is anticipated that  $\sim 720,000$  family linked offspring would be observed for Norway and  $\sim 660,000$  for Denmark. The corresponding estimates of family linked offspring with paternal exposure to valproate monotherapy would be  $\sim 860$  and  $\sim 790$  respectively. Assuming a similar number of family linked offspring with paternal exposure to the composite monotherapy reference AED group are available to achieve a total cohort size of  $\sim 1720$  for Norway and 1580 for Denmark, these numbers would be more than sufficient to permit the observation of the aforementioned effect size of 2.5 for major CM assuming a background risk of 3%, with 80% power.

Since the paternal record linkage for pregnancies with outcomes reported prior to birth is not feasible for Sweden all relevant CM analysis are presented separately

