### 9.2.1 Study time period

The study time period will be based on availability of information from the National Registries; this will start from 01 January 2007 in Sweden, 01 January 2010 in Norway, and 01 January 1997 (01 April 2004 for secondary outcome) in Denmark in order to allow for 24 months average look back period for live births:

- pregnancy duration (9-months on average for live births),
- maternal and paternal preconceptional exposure (3-months),
- minimum look back period for confounders (12-months).

The study time period ends on 31 December 2018 for Denmark and 31 December 2019 for Sweden and Norway. The rationale for this choice is to include all data available from relevant

 In Denmark, for the period 1997-1 April 2004, stillborns born between 22nd and 28th weeks of gestation are not included in the Medical Birth Register but in the National Patient Register. However, since in the National Patient Register the linkage with the father is not available, the study period for the secondary outcome in Denmark is limited to 2004-2017 (or last available date).

linked registers, to capture a sufficient number of outcomes and exposures and linked family units, and to include the most up-to-date data available.

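### Section 9.5 does not apply its 50% linkage scenario to Norway and still uses superseded birth periods; once corrected, Norway's worst-case CM cohort falls below the 413 per group required

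*Protocol*

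**What the plan says.** Section 9.5 lists its inputs: "Total births for study period: Norway 2004-2017" at about 0.8M, Denmark 1995-2017 at about 1.3M, Sweden 2005-2017 at about 1.5M, and valproate monotherapy at 1.2 per 1000. For NDD and ASD it assumes at least 95% family linkage and a 0.15% childhood AED/epilepsy exclusion. It projects 940, 1495 and 1645 exposed offspring for Norway, Denmark and Sweden (4,080 pooled), and concludes that "this study should have a sufficient number of paternally exposed valproate offspring within each country to observe a HR of 2.0 for the primary endpoint".

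For CM it uses a different linkage figure. It notes that linkage is about 97% for live births but lower for non-live births, and continues: "Assuming a worst case scenario of 50% of pregnancies with record linkage, it is anticipated that" about 720,000 "family linked offspring would be observed for Norway and" about 660,000 for Denmark. That gives about 860 and 790 exposed offspring, and cohorts of about 1720 and 1580 with an equal comparator group. Both are called comfortably enough for an effect of 2.5 at 3% background risk with 80% power, for which the section requires 413 per group.

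Section 9.2.1 sets the current study period: "01 January 2010 in Norway, and 01 January 1997" in Denmark, with 01 April 2004 for the Danish secondary outcome and 2007 for Sweden. It ends on 31 December 2018 in Denmark and 31 December 2019 in Norway and Sweden.

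**The concern.** A single worst-case factor should leave Norway, with 0.8M births, with fewer linked offspring than Denmark with 1.3M. The text gives Norway more. Separately, two current sections disagree on which birth years the study covers: section 9.2.1 was moved to the shorter Norwegian window, while the section 9.5 projections were not.

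The comparative analyses are first run by country (section 9.7.1). A reader of a null Norwegian CM result would judge it against a projected 860 exposed offspring, about 2.5 times what the plan's own inputs support in its worst case (860/343 = 2.5).

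**Working it through.** **Reproducing the plan's figures**

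- Exposed offspring: 720,000 x 0.0012 = 864 (stated about 860); 660,000 x 0.0012 = 792 (stated about 790). The exposure step is therefore consistent, and 720,000 is not a misprint confined to one number.
- Linkage: 660,000 / 1.3M = 51%, so the factor was applied to Denmark. 720,000 / 0.8M = 90%, so it was not applied to Norway.
- A possible source, by inference only: the births implied by Sweden's 1645 are 1645 / (0.95 x 0.0012 x 0.9985) = 1.445M, and half of that is about 722,600.
- Required size: the 413 comes from the arcsine approximation to Fisher's exact test, two-sided 5%, 1:1, with power = Phi( sqrt(2n) x [asin sqrt(p2 - 1/(2n)) - asin sqrt(p1 + 1/(2n))] - 1.96 ). This returns totals of 826 (3%, ratio 2.5), 1178 (4%, ratio 2) and 3252 (1.5%, ratio 2), as in the plan. All power figures below use it.

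**Step 1: apply 50% to Norway, old period**

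0.8M x 0.5 = 400,000 linked; x 0.0012 = 480 exposed. This still exceeds 413, with power 86%.

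**Step 2: use the current periods as well** (constant births per year assumed)

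- Norway 2010-2019, 10 of the 14 years counted: 0.8M x 10/14 x 0.5 x 0.0012 = 343. Power 71%.
- Denmark April 2004-2018, 14.75 of 23 years: 1.3M x 14.75/23 x 0.5 x 0.0012 = 500. Power 88%.
- Pooled: 343 + 500 = 843 per group. Power about 98%.

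| CM, per group | Stated | Corrected | Required | Power |
|---|---|---|---|---|
| Norway | about 860 | 343 | 413 | 71% |
| Denmark | about 790 | 500 | 413 | 88% |
| Pooled | about 1650 | 843 | 413 | about 98% |

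**Sensitivity for Norway**

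- Births implied by the stated 940: 940 / (0.95 x 0.0012 x 0.9985) = 825,800. This gives 354 exposed and 73% power.
- The pooled two-proportion formula gives 75% to 77% for 343 to 354, but it does not reproduce 413.
- Linkage needed over ten years: 413 / (0.0012 x 0.8M x 10/14) = 60%. At the 97% that section 9.4.1 reports for Norway, the count is 665 and power is 95%.

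**Effect of the period change on NDD and ASD** (95% linkage; the 50% factor plays no part)

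- Norway: 940 x 10/14 = 671, against 589 required at 4%. Power 85%.
- Denmark: 1495 x 22/23 = 1430. Power 99%.
- Sweden: 13 years before and after, so 1645 is unchanged. Power above 99%.
- Pooled: 671 + 1430 + 1645 = 3,746, against 1627 required for ASD at 1.5%. Power 99%.

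**The case against.** The strongest defence is that little depends on this paragraph. CM is secondary, and the section says a formal sample size does not apply and offers the evaluation for completeness. The linkage slip alone leaves Norway above 413, so the shortfall needs both corrections and a deliberately pessimistic linkage. At the 97% reported for Norway the power is about 95%. CM is pooled with Denmark, where power is about 98%. The study is retrospective, so no recruitment depends on the projection. All of this stands, and it limits the severity. It does not make the printed Norwegian figures or the Norwegian conclusion correct under the scenario the section itself chose.

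A reader might go further in two directions that the document does not support.

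- **The per-country NDD claim fails.** At the plan's 4% risk Norway still has 671 against 589. A failure appears only at the 3% end of the 3-4% range in section 9.5, where Table 6 requires 1592/2 = 796 and power is 72%. That is a different choice of assumption, and the plan's statement is conditional on its projections being observed.
- **ASD is underpowered, because the 1.5% risk comes from 14 years of follow-up while children here are followed to 12, or 10 in Norway.** Lower risks do reduce power at 1627 per group, but 1627 is the minimum requirement and the projected cohort is 3,746. At reference risks of 1% and 0.75% the requirements are 2455 and 3285 per group, both below 3,746, and power is 94% and 85%. This assumes a comparator group of equal size.

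**Conclusion.** The point holds for the CM projection. Section 9.5 misstates Norway's worst-case linked and exposed numbers (720,000 and 860 instead of 400,000 and 480 on its own birth count), and it projects both countries from periods that section 9.2.1 has replaced. With both corrected, Norway has about 343 per group against 413, with about 71% power, so the 80% claim is wrong for Norway alone in the stated worst case. Denmark drops from about 790 to about 500 and remains adequate.

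These figures rest on constant births per year, 1.2 exposed per 1000, an equal comparator group, and no deduction for the later parental and maternal exclusions. The document does not support extending the conclusion to the per-country NDD statement at 4%, to pooled ASD, or to the pooled CM analysis. This should be fixed; it does not threaten the design.

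**What to change.** In section 9.5:

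- Recompute every projection with the section 9.2.1 periods, and apply the 50% factor to both countries. Assuming constant births per year, replace 720,000 / 860 / 1720 for Norway with about 286,000 / 343 / 686, and 660,000 / 790 / 1580 for Denmark with about 417,000 / 500 / 1,000. Actual births for the current years would be better than pro-rating.
- Limit the CM sufficiency statement to Denmark and to the pooled Norway and Denmark estimate (about 843 per group). State that Norway alone falls short of 80% at 50% linkage and would need about 60%.
- Update the NDD projections to about 671 (Norway), 1430 (Denmark), 1645 (Sweden) and 3,746 pooled. Keep the per-country NDD and pooled ASD statements. A note that Norwegian NDD power is about 72% at a 3% reference risk is optional.

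The requirements quoted in the abstract (1178 and 826) need no change. The cost is edited text in one section, with no change to data, design or analysis.
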